Anticipated dates of launch in planned participating countries	From Q3 2017 to Q4 2019 (depending on market access conditions):
	• Germany, UK: Q3 2017
	 Denmark, Norway: Q4 2017
	• Spain, Sweden, The Netherlands: Q1 2018
	Australia: Q2 2018
	 Belgium, Finland, France: Q3 2018
	 Czech Republic, Italy, Switzerland: Q4 2018
	• Turkey: Q2 2019
Institutional review board (IRB) approvals by country, according to national regulations	Up to 9 months after protocol approval (anticipated dates for the first approvals in Q3 2018)
Start of data collection	As soon as possible after all necessary approvals have been received in a specific country (anticipated start dates for the first countries in Q3 2018)
End of data collection	15 years after start of the data collection (anticipated in Q3 2033)
First interim report	3 years after start of data collection (anticipated in Q3 2021), with data collected over the first 2 years
Second interim report	6 years after start of data collection (anticipated in Q3 2024), with data collected over the 5-year period anticipated for patient recruitment
Third interim report	9 years after start of data collection (anticipated in Q3 2027)
Fourth interim report	12 years after start of data collection (anticipated in Q3 2030)
Final report of study results	Anticipated in Q3 2034, at the latest 1 year after the end of data collection
Study progress updates	To be submitted according to periodicity of each PBRER

7 Rationale and Background

Epidemiology of Multiple Sclerosis

Multiple sclerosis (MS) is an immune-mediated, chronic inflammatory disease of the central nervous system (CNS) characterized by the demyelination and destruction of axons (Tullman, 2013). With no definite cause established, MS has been hypothesized to result from a complex interaction between individual genetic susceptibility and environmental factors that act as triggers of a self-sustained auto-immune response (Noseworthy, 2000). With a peak of onset averaging at the age of 30 years in both genders, MS occurs predominantly in women with a female:male ratio of 3:1 (Kingwell, 2013).

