9.1 Study Design

9.1.1 Design Overview

The PASS is a multi-country, multi-center, long-term, prospective, observational study evaluating the safety in patients with highly active R(R)MS newly initiating oral cladribine (cladribine cohort) as compared to highly active R(R)MS patients newly initiating fingolimod (comparator cohort). Fingolimod has been selected as the comparator for this study given that both cladribine and fingolimod have oral administration and target a very similar indication, thereby minimizing possible confounding bias by indication and selection bias.

[figure not shown]
The study is projected to last for a maximum of 15 years, with a maximum 5-year recruitment period and a follow-up of 10 years for each patient. For each patient, data collection will begin after the signature of the informed consent form – noting that patient consent applies to all countries in which additional primary data collection will be conducted and to some countries where secondary use of data will be performed – and continue during 10 years as each patient will be followed for a period of 10 years, except if s/he is lost to follow-up, or withdraws his/her consent, or dies before the end of the follow-up period. Follow-up will continue regardless of oral cladribine or fingolimod discontinuation.

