9.2.1.2 Additional Primary Data Collection

Additional primary data collection will be set up in selected sites from the network of neurological centers contributing to the MSDS 3D and NeuroTransData (NTD) database. The sites are primarily located in Germany with additional sites in Switzerland and Spain.

Eligible patients will be included in the study by the treating physicians who manage MS patients in participating sites from the pre-existing registries at the time of presentation for a routine clinic visit. The pre-existing registries in this situation act as a network of neurological centers. All R(R)MS patients newly initiating oral cladribine or fingolimod during the enrolment period will be assessed for eligibility and all eligible patients will be consecutively proposed to enter the study. After signing the informed consent, the additional primary data is collected directly from the patient by the treating physician using an electronic data capture system specifically designed for the purpose of this study or using an existing data collection system augmented with study-specific modules to capture information not readily available in the existing data collection system (additional data collection).

The specifications of the electronic data capture system/additional modules will be developed according to the study protocol and will be used to capture all the variables required specifically for the study.

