9.2.4 Study Period

Cohort entry date is defined as the date a patient newly initiates cladribine or fingolimod. The cohort entry date can only be after cladribine has become available in the country participating to the study.

In the data sources using additional primary data collection, patients will be followed from the cohort entry date after they have signed the informed consent until the end of the data collection period (10 years), loss to follow-up, withdrawal of their informed consent or death, whichever comes first. In the data sources with secondary use of data only, patients will be followed from the cohort entry date until the end of the data collection period (10 years), emigration, or death, whichever comes first. The overall study duration is estimated to be of maximum 15 years in both cohorts, based on an estimated recruitment period of 5 years and a follow-up of 10 years for each patient.

Due to the prolonged action of oral cladribine and the potentially long latency period of some of the study outcomes, patients who discontinue the study treatment will still be followed until the end of the 10-year period after enrolment, even if the patients switches to any other DMT.

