9.8.2 Derived and Transformed Data

Calculation of person-years of follow-up

Follow-up time for each patient will be calculated from the cohort entry date (initiation of oral cladribine or fingolimod) to the earliest of the following: event of interest, death, end of follow-up, withdrawal of informed consent, emigration or loss to follow-up. For a given non-recurrent event (e.g. first malignancy), the patient follow-up will not be censored for the other events of interest, and the patient will continue to contribute to the risk time for these other events.

Severe lymphopenia duration

Severe lymphopenia duration is defined as the interval from the finding of severe lymphopenia (Grade \geq 3) until the finding of its resolution (Grade 1 or 0). Given that no regular blood tests are requested per protocol, there is a risk to overestimate the duration of lymphopenia. However, in patients with severe lymphopenia, this risk of bias will be reduced because the physician would be expected to perform a closer follow-up with more frequent blood testing.

Handling of missing data

Methods commonly used in non-interventional studies for handling missing data will be applied. Descriptive analyses will be performed using available data. The number of patients with missing data will be reported for each measured variable in the study. In descriptive analyses, missing data will be described separately and not included in the denominator for the calculation of the percentage for each category of a particular variable.

Full details on handling missing data will be described in more detail in the SAP which will describe the methods for identifying where missing data methods should be applied, the techniques for identifying the type of missing information and the appropriate imputation methods to be used, if any, as per European Medicines Agency (EMA) 2011 guidance on missing data.

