- ¹⁾ Life-threatening in this context refers to a reaction in which the patient was at risk of death at the time of the reaction; it does not refer to a reaction that hypothetically might have caused death if more severe.
- ²⁾ Medical and scientific judgement should be exercised in deciding whether other situations should be considered serious reactions, such as important medical events that might not be immediately life threatening or result in death or hospitalisation but might jeopardise the patient or might require intervention to prevent one of the other outcomes listed above. Examples of such events are intensive treatment in an emergency room or at home for allergic bronchospasm, blood dyscrasias or convulsions that do not result in hospitalisation or development of dependency or abuse.

Any suspected transmission via a medicinal product of an infectious agent is also considered a SAE/SAR.

Adverse Events of Special Interest (AESI)

An AESI is an AE of scientific and medical concern specific to the Sponsor's product or program, for which ongoing monitoring and rapid communication by the investigator to the Sponsor can be appropriate. In this study, severe infections, tuberculosis, PML, other opportunistic infections, malignancies, and severe lymphopenia are considered AESI. AESI should be reported following the procedure described in Section 11.4.

Events Not to be considered as AEs

Medical conditions present in a patient and documented at the time of study enrolment, and that do not worsen in severity or frequency during the study, are defined as baseline medical conditions, and are NOT to be considered as AE.

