11.4 Recording of Adverse Events

In this study, will be recorded:

- All ARs (ie, events suspected to be related to oral cladribine or fingolimod)
- AESI (severe infections, herpes zoster infection, tuberculosis, PML, other opportunistic infections, malignancies, and severe lymphopenia,) (ie, all such events regardless of the suspected causal relationship to oral cladribine or fingolimod)
- Any fatal cases (ie, all fatal events regardless of the suspected causal relationship to oral cladribine or fingolimod)

In line with the provisions of GVP Module VI rev 1, it can be justified that not all AEs that occur during the course of this PASS need to be collected. Indeed, the known safety profile of oral cladribine has been established based on a large integrated safety data set, including data from

placebo-controlled clinical trials. The majority of AEs are expected to be related to the underlying disease (multiple sclerosis) and would not add meaningful new safety information to the known safety profile of cladribine. As a consequence,

- The main focus of this long-term PASS is to monitor and further characterize the important identified and potential risks of oral cladribine. For these events, AESI will be collected regardless of causal relationship for a 4-year period after treatment initiation.
- In addition, the potential risk of malignancies will be followed for 6 additional years for each patient (so during 10 years in total).
- Furthermore, any AR suspected to be related to cladribine or fingolimod and any fatal cases regardless of causality will be collected during the full study follow-up period (10 years for each patient).

The recording period begins, when the patient is initially enrolled in the study (date of signature of informed consent). Recording will be continued as follows:

- AESI (except malignancies, see below) regardless of causality: 4 years after the enrolment of a patient, which is in line with the SmPC, ie, 2 years treatment in Years 1 and 2 and no further cladribine treatment in years 3 and 4. This period is in line with the duration of cladribine efficacy of at least 4 years.
- AESI of Malignancies (regardless of causality): 10 years after the date of signature of informed consent (duration of the complete patient follow-up)
- ARs: 10 years after the first dose of oral cladribine (duration of the complete patient follow-up)

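### In NTD and MSDS 3D, person-time starts at treatment initiation but AESI recording starts at consent, so any gap between the two dates biases incidence rates downward

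*Protocol*

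**What the plan says.** **Start of risk time.** Protocol 9.2.4: "Cohort entry date is defined as the date a patient newly initiates cladribine or fingolimod". Section 9.8.2 builds the denominator on that date: "Follow-up time for each patient will be calculated from the cohort entry date (initiation of oral cladribine or fingolimod". It makes no exception for patients who consent later.

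**Start of recording.** Protocol 9.1.1, for sources where consent applies: "For each patient, data collection will begin after the signature of the informed consent form". Section 11.4: "The recording period begins, when the patient is initially enrolled in the study (date of signature of informed consent". The introduction to Section 11 confines its detailed recording rules to sources with additional primary data collection, which Section 9.1.1 names as NTD and MSDS 3D.

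**Enrolment has two meanings.** The Abstract (Variables) and Section 9.3.1 equate it with treatment initiation; Section 11.4 equates it with consent. Section 9.2.4 puts both dates into one phrase for the primary-collection sources. Section 11.4 itself counts the 4-year AESI period once from treatment initiation and once from enrolment, and the 10-year malignancy period from consent.

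**When patients enter.** Section 9.2.1.2 has physicians include patients "at the time of presentation for a routine clinic visit". Section 9.2.3 places the prescribing decision before the decision to include.

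**What counts as baseline.** Section 11.1 does not treat as adverse events those conditions that do not worsen and fit this description: "Medical conditions present in a patient and documented at the time of study enrolment".

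**The concern.** An incidence rate needs numerator and denominator to open on the same day. Here the denominator opens at first treatment and, in NTD and MSDS 3D, the numerator opens at consent. If consent comes later, the interval adds person-time but cannot add events, and a patient who dies before consent never enters.

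Section 9.8.3 makes the cohort-specific AESI rates part of the primary analysis, so a bias in the rate alone touches the primary objective. The early weeks may also matter. Section 9.2.3 places both year-1 cladribine treatment weeks in the first two months, and Section 7 reports more herpes zoster during Grade 3 or 4 lymphopenia. If enrolment is read as consent, an infection between first dose and consent could be filed as medical history, which under Section 9.3.1 includes zoster and prior severe or opportunistic infections. The only early-window sensitivity analysis in Section 9.8.3 is for malignancy; zoster and the infections have none.

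**Working it through.** **Plan's own figures.** The protocol gives no figure for the initiation-to-consent interval. The nearest related figure, the 62% in Table 4 (year 15, background 0.40 per 100 PY, 32,907 PY, true RR 1.3), reproduces at 62.2% by simulation with mid-P limits. The study-size tables are not in question.

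**Inputs from the protocol.** Risk time from initiation (9.2.4, 9.8.2); recording from consent (11.4); a 4-year window for non-malignancy AESIs and 10 years for malignancy (11.4); routine visits about every 3 months in Germany and Switzerland and every 6 months in Spain (9.1.1).

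**Assumptions.** Gap g of 0, 3 or 6 months (the visit spacing serves only to bound it); constant hazard unless stated; share s of the cohort that comes from affected sources, which the protocol does not give.

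**Step 1: rate among affected patients.** Observed/true rate = 1 − g/T, with T the follow-up.

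| Gap g | T = 12 months | T = 48 months | T = 120 months |
|---|---|---|---|
| 0 | 1.00 | 1.00 | 1.00 |
| 3 months | 1 − 3/12 = 0.75 | 1 − 3/48 = 0.9375 | 1 − 3/120 = 0.975 |
| 6 months | 1 − 6/12 = 0.50 | 1 − 6/48 = 0.875 | 1 − 6/120 = 0.95 |

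If follow-up averages what Table 3 projects (32,907/4,000 = 8.23 years, or 98.7 months), the malignancy losses become 3/98.7 = 3.0% and 6/98.7 = 6.1%.

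**Step 2: dilution.** In the whole cohort the factor is 1 − s·g/T. With s = 0.25 and g = 3, the loss is 0.25 × 3/12 = 6.25% over 12 months and 0.25 × 3/48 = 1.6% over 4 years.

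**Step 3: rate ratio (cladribine/fingolimod).** Observed/true IRR = (1 − s·gC/T)/(1 − s·gF/T), with gC and gF the gaps in the cladribine and fingolimod cohorts.
- Equal gaps, equal s, constant hazard: 1.00.
- gC = 0, gF = 3, s = 0.25: 1/(1 − 0.0625) = 1.07 over 12 months; 1/(1 − 0.0156) = 1.02 over 4 years.
- The same gaps with s = 1: 1/0.75 = 1.33 and 1/0.9375 = 1.07.
- Equal 3-month gaps, s = 1, cladribine hazard assumed doubled in months 0–6. Over 12 months cladribine keeps (3×2 + 6)/(6×2 + 6) = 12/18 = 0.667 of its events and fingolimod 0.75, a factor of 0.89. Over 48 months, 48/54 = 0.889 against 0.9375, a factor of 0.95.

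**Step 4: after correction.** If risk time opens at the later of initiation and consent, events and person-time both cover T − g, and the ratio in Step 1 is 1.00 for any gap under constant hazard. Collecting events back to initiation gives the same for patients who reach consent.

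**The case against.** The strongest reply is that the intended gap is zero. The Abstract and Section 9.3.1 define enrolment as treatment initiation. Section 9.10 has primary-collection sites enrol prospectively and invite consecutive patients. The routine visit may be the visit at which treatment starts, and Section 9.2.3 puts the prescribing decision, not the first dose, ahead of inclusion. Section 11.4 also says in one place that AESIs are collected for four years from treatment initiation. NTD already holds data recorded at least quarterly (Appendix 2), so events before consent need not be lost. The baseline clause in 11.1 concerns conditions present at enrolment, and a resolved zoster episode is not plainly one.

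Much of this stands: no gap is documented, and bias is not proven. It does not remove the point. Equating enrolment with initiation in one section contradicts Section 11.4 rather than overriding it, and nothing requires consent by the first dose or states that earlier events are captured. Nor can this be left wholly to the SAP, because 9.8.2 and 11.4 already fix the two start dates.

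Three stronger readings are tempting but unsupported:
- **All consent-based sources are affected.** A reader might extend the point to MSBase and OFSEP. Their additional consent concerns transfer of data to another organization (9.2.1.1), secondary-only patients are followed from cohort entry (9.2.4), and every recorded entry is captured (9.2.5).
- **German patients carry a 12-month gap.** A reader might combine "The cohort entry date can only be after cladribine has become available in the country participating to the study" with the launch date in Section 6, "Germany, UK: Q3 2017", and a first data-collection start in Q3 2018. But the first is only a lower bound, and Section 9.2.1.2 limits assessment at these sites to patients who initiate during the enrolment period.
- **The rate ratio must be biased.** Step 3 shows that it need not be.

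**Conclusion.** The point holds for NTD and MSDS 3D. The protocol gives inconsistent start dates for risk time and event recording, with no delayed-entry rule, no cap on the interval and no back-capture. Any positive interval lowers the observed AESI rates there. The size rests on assumptions: for gaps of 3 to 6 months at constant hazard, 25–50% over the first year, 6–12.5% over the 4-year AESI window and 2.5–5% over 10 years among affected patients. These figures shrink in proportion to the unknown share of such patients and vanish if the gap is zero.

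Bias in the cladribine–fingolimod ratio is conditional on gaps, source mix or early hazards that differ between cohorts. For malignancy, which drives study size, the effect is small and early exclusions are planned. Infections and herpes zoster have the larger exposure and no equivalent check.

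**What to change.** Reconcile the Abstract (Variables) and Sections 9.1.1, 9.2.4, 9.3.1, 9.8.2, 11.1 and 11.4 so that enrolment, cohort entry and consent are three distinct, consistently used dates. Then, in 9.8.2, for the sources with additional primary data collection, choose one rule:

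1. Start risk time at the later of initiation and consent (delayed entry), with time since initiation as the time scale; or
2. Ascertain AESIs back to the first dose and count them as outcomes, with baseline in 11.1 and 11.4 set at treatment initiation.

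Under either rule, record the consent date and report the initiation-to-consent interval by cohort.

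**Cost.** Mostly wording. Section 11.4 already uses the consent date as a clock, but Section 9.3.1 does not list it as a variable, so it must be added. Rule 1 gives up some early person-time, which may be an informative window. Rule 2 keeps that window but requires retrospective capture and cannot recover patients who die before consent. The choice is best made before data collection, because early events that are not collected may not be recoverable.

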9.2.5 Frequency of Assessments

No additional visits to the HCP outside of routine practice will be mandated by the protocol. Data collection is conducted according to local routine medical practices and data are captured during routine clinic visits. However, it is expected that data will be collected with a periodicity of at least 6 months over the full study period, based on current practices regarding management of patients with R(R)MS in Europe and other participating countries. Study outcomes (malignancies, severe and/or serious infections, opportunistic infections, lymphocyte counts [if performed according to routine practice], treatment discontinuation and reasons for discontinuation) will be mandatory variables and will be collected during each routine clinical visit. In the data sources with secondary use of data, the data collection will be event-based: the data collected will include only the variables the physician has considered as relevant to be recorded during the visit. All entries recorded in these data sources will be captured. In this real-world setting, the frequency of visits is also expected to be dictated by disease complications or occurrence of AEs.

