9.7.3 General Data Management

Following data extraction from the data sources (secondary alone or complemented with primary collection), the transferred data will be stored in a raw data repository managed by the CRO under a secure server for data validation and data cleaning procedures. In order to ease the management of data collected from the different data sources participating to the study, an electronic data capture (EDC) system will be used as a central database for all the study data. Data collection modules in the central database will enable the consolidation of the extracted datasets from each of the data sources. This approach will also allow logic checks and data validation checks at the time of data import for swifter identification of any inconsistencies in the data received.

A data migrator tool within the EDC system will be used to map the source data to a consolidated, unified format. It has been identified that some of the data can be collected in the correct format already from the source. Data validation checks can thereby be done during the upload and batch edit checks after the data is merged in the EDC database ensuring further data consistency. The flow chart presented below (Figure 5) describes the process where core data refers to the study variables and outcomes including AESIs collected by the different data sources of the study. The safety reporting track which is applicable only for data sources with additional data collection is highlighted in yellow and described according to the safety reporting requirements in section 11.5. Data extractions for aggregate-level review listings and study progress will be conducted as needed.

Figure 5 Overall data flow from data collection to central EDC database including safety reporting track.

EDC: Electronic Data Capture.

A Data Management plan will be developed to describe all data management processes.in detail and all steps necessary from raw data to final database such as, but not limited to, database development, additional primary data collection process, process for secondary use of data, medical coding considerations and conventions, query edition and database validation.

The Data validation plan will be edited, describing in detail all data checks to be performed on completeness, plausibility and consistency of collected data and identification of data discrepancies and query management based on data cleaning procedures.

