9.8.3 Statistical Methods

Descriptive analyses

For continuous variables, the following measures will be reported: the number of patients with non-missing data, the number of patients with missing data, mean, standard deviation, median, quartiles, and minimum and maximum. For categorical variables, the number of non-missing observations (number and percentage of total non-missing; n, % of total), as well as the number of patients with missing data will be reported.

Description of analysis sets and characteristics at enrolment

Number and percentage of patients per cohort (cladribine or fingolimod) will be presented by analysis sets as well as by participant country.

The description of demographic characteristics and other characteristics at enrolment for both cohorts will be presented using summary tables to allow a general comparison. Appropriate statistical tests will be applied to compare the cohorts. Further details on methodology will be provided in the SAP.

Assessment and comparison of safety outcomes

Primary analysis

Using the intention-to-treat exposure definition, the crude and adjusted incidence rates of the different AESIs along with 95% CIs will be estimated in both oral cladribine patients and fingolimod patients. The following categories of AESI will be considered: malignancies (excluding NMSC), herpes zoster infections, tuberculosis, PML, other opportunistic infections, and other severe infections.

To compare the incidence of AESI between oral cladribine patients and fingolimod patients adjusting for key prognostic factors (as defined *a priori* in the SAP for each AESI), the incidence rates ratios of the AESI together with the 95% CIs will be estimated by Poisson regression models

adjusted for the key prognostic factors (including prior use of immunomodulatory/immunosuppressive agents) and displayed by means of forest plots.

Sensitivity analyses for the primary analysis

The following sensitivity analyses will be performed for the primary analysis:

- 1) For the analyses regarding malignancies, 2 sensitivity analyses excluding all malignancies occurring within 6 and 12 months after cohort entry will be performed to account for the latency period for malignancies to develop (induction period of 6 and 12 months after treatment initiation).

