10.2 Patient Identification and Privacy

Data protection and privacy regulations will be observed in capturing, forwarding, processing, and storing subject data.

The CRO will maintain information on the study individuals securely on site according to up-to-date standard operating procedures. The CRO will also maintain appropriate data storage, including periodic backup of files, and archiving procedures (see Section 9.11.4). The CRO will comply with procedures that include checking electronic files, maintaining security and data confidentiality, following analyses plans, and performing quality checks for all programs. The Sponsor or other parties outside the CRO cannot receive access to individual-level data. Only aggregated results will be presented to the Sponsor or otherwise published.

11 Management and Reporting of Adverse Events

The management and reporting of adverse events (AEs) varies according to the study model in the country concerned, which can be based on:

- either secondary use of data only,
- or secondary use of data supplemented by primary data collection (mixed model).

According to EU GVP module VI rev 1, non-interventional studies based on secondary use of data (as in the Nordic countries and MSBase) do not require reporting of suspected adverse reactions in the form of Individual Case Safety Reports. Safety data will then be summarised in the interim and final study reports.

In countries where existing registries are supplemented by additional primary data collection, the management and reporting of AEs are described below. In these countries, safety data will mainly be collected via the module specifically designed for the study purpose.

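### Infection AESIs: person-time runs to Year 10, but Section 11.4 limits recording regardless of causality to 4 years in the primary-collection sources, against Sections 9.2.5 and 9.4.2

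*Protocol*

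**What the plan says.** **Denominator.** Protocol Section 9.8.2 counts each patient's time from cohort entry to the earliest of "event of interest, death, end of follow-up, withdrawal of informed consent, emigration or loss to follow-up". Its only event-specific rule is that a non-recurrent event does not censor the others; infections have no Year-4 stop. Section 9.2.4 sets follow-up at 10 years, also after stopping drug: "patients who discontinue the study treatment will still be followed until the end of the 10-year period after enrolment".

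**Numerator, Section 11.4.** For the important risks, "AESI will be collected regardless of causal relationship for a 4-year period after treatment initiation". The limit is repeated in the list of recording periods, with a reason (the label and the duration of efficacy), while malignancies get six further years. Over the full 10 years, "any AR suspected to be related to cladribine or fingolimod and any fatal cases regardless of causality will be collected". The opening of Section 11 confines these rules to sources with additional primary collection, where "safety data will mainly be collected via the module specifically designed for the study purpose". Section 9.1.1 names these as NTD and MSDS 3D.

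**Numerator, Section 9.** Section 9.2.5 makes severe, serious and opportunistic infections mandatory items at each routine visit and expects that "data will be collected with a periodicity of at least 6 months over the full study period". Section 9.4.2 has infections of every microbial class recorded over the study period. Section 9.7.3 says that "core data refers to the study variables and outcomes including AESIs collected by the different data sources", with no stop date.

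**Use.** Section 9.8.3 makes crude and adjusted rates of each AESI a primary output. For the comparison, "the incidence rates ratios of the AESI together with the 95% CIs will be estimated by Poisson regression models". Five of the six AESI categories listed there are infections.

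**The concern.** A rate needs events and person-time from the same window. Read literally, Section 11.4 closes the window for complete infection recording at Year 4 in some sources, while Section 9.8.2 keeps adding person-time until Year 10. Infection rates from those sources would be too low. Pooled rates would then depend on how many patients come from each type of source, since the secondary-use sources have no such limit.

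After Year 4 a non-fatal infection would enter only if someone suspected a drug cause. That judgement could differ between fingolimod taken daily and cladribine, whose recommended courses end in the second year (Section 9.2.3). At stake are herpes zoster, tuberculosis, PML, other opportunistic infections and other severe infections. An analysis plan can shorten person-time afterwards, but it cannot restore events that were never recorded.

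**Working it through.** **Inputs.** 4,000 patients per cohort and about 5% drop-out a year (Section 9.6); 10-year follow-up (Section 9.2.4); 4-year window (Section 11.4); 32,907 person-years per cohort at Year 15 (Table 3). The share of patients in the primary-collection sources, p, is not given and is an assumption. So is q, the fraction of infections after Year 4 that are still recorded as suspected reactions or fatal cases.

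**The plan's own figure.** With annual steps, 4,000 × (1 − 0.95^10)/0.05 = 32,101 person-years, within 3% of 32,907, so the drop-out assumption is a fair basis. The protocol gives no precision figure for infections.

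**Share of person-time after Year 4.** Person-years per patient to time T = (1 − 0.95^T)/(−ln 0.95).
- T = 4: 3.616
- T = 10: 7.823
- Share up to Year 4: 3.616/7.823 = 0.462, so 0.538 lies later.
- Drop-out fitted to Table 3: 32,907/4,000 = 8.227 person-years each, implied hazard 0.0404, share up to Year 4 = 0.449.
- No drop-out: 4/10 = 0.40.

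**Rate within those sources.** At a constant true rate, observed/true = 0.462 + 0.538q:
- q = 0: 0.46 (worst case)
- q = 0.25: 0.60
- q = 0.50: 0.73

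**Pooled rate.** With complete capture elsewhere, observed/true = 1 − 0.538p(1 − q):

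| p | q = 0 | q = 0.25 | q = 0.50 |
|---|---|---|---|
| 10% | 0.95 | 0.96 | 0.97 |
| 25% | 0.87 | 0.90 | 0.93 |
| 50% | 0.73 | 0.80 | 0.87 |

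For scale, the trial zoster rate of 0.86 per 100 person-years in Section 7 would read 0.74 at p = 25% and 0.63 at p = 50%, both with q = 0.

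**Rate ratio.** With constant rates and equal drop-out, the same p and q in both cohorts cancel and the ratio is unchanged. Otherwise, for a true ratio (cladribine to fingolimod) of 1 and assumed inputs:
- Source share 40% cladribine, 20% fingolimod, q = 0, source not adjusted for: (1 − 0.538 × 0.4)/(1 − 0.538 × 0.2) = 0.88. Reversed shares: 1.14.
- Late capture 10% cladribine, 50% fingolimod, within those sources: 0.516/0.731 = 0.71. With 50% and 25%: 0.731/0.597 = 1.23.

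These values show only that the direction is open; none is an estimate for this study.

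**The case against.** The strongest reply is that the protocol runs two tracks. Section 9.7.2 has the study modules capture every variable the study needs and adds a safety module for reporting adverse drug reactions. Section 9.7.3 keeps core data, which include AESIs, apart from a safety reporting track that exists only in the primary-collection sources. Section 9.3.2 lists the outcomes with no stop date, Section 9.4.2 has infections recorded over the study period, and Appendix 2 makes recording of all study variables mandatory in NTD and MSDS 3D. On this reading the 4-year window limits pharmacovigilance only, infection outcomes run for 10 years, and Section 9.8.2 is right as it stands.

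That reading is coherent, and it stands as a possibility. The protocol never says so, however. Section 11.4 speaks of what is collected and recorded, with reporting treated separately in Section 11.5, and the opening of Section 11 makes the module the main route for safety data in these sources. The mandatory list in Section 9.2.5 also does not name non-severe zoster, although zoster of any severity is a primary outcome.

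Two further objections stand. Suspected reactions and fatal cases are still recorded after Year 4, so 46% is a floor at 5% drop-out. And adjustment for data source is not excluded, because Section 9.8.3 leaves the covariates for each AESI to the SAP.

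**Conclusion.** The contradiction is real and needs a decision. Data loss is possible but not established. If Section 11.4 governs outcome collection, about 54% of 10-year person-time in the primary-collection sources lacks complete infection capture (55% with drop-out fitted to Table 3). Infection rates there could then be as low as about 46% of the true value, assuming a constant rate, 5% yearly drop-out and nothing recorded after Year 4. The effect on pooled rates cannot be fixed without the source shares. Malignancy analyses, and Tables 3 and 4, are untouched.

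A reader might infer more in three ways, and the documents support none of them:
- **That late infections will be lost.** Sections 9.2.5, 9.4.2 and 9.7.3 point the other way.
- **That the cladribine-to-fingolimod ratio is biased.** This needs a difference between cohorts in source mix or late capture, and the documents give neither.
- **That a single zoster ratio over all follow-up is itself an error because dosing falls in the first two years.** The intention-to-treat average is a valid summary. No zoster rate by year and no fingolimod zoster rate is given, so a changing ratio is not shown. The as-treated, on-treatment, time-since-last-dose and cumulative-incidence analyses, the first interim report and the lymphopenia analysis cover timing in part. Splitting the model by period is detail that a protocol may leave to the SAP.

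**What to change.** State in Section 11.4 whether the 4-year window limits safety reporting only or also outcome collection, and align Sections 9.2.5, 9.4.2 and 9.8.2 with the answer.

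- **Reporting only.** Say that infection outcomes, including zoster of any severity, are recorded regardless of causality for 10 years in every source. If sites already work this way, the change is wording only; if not, it adds recording work at the primary-collection sites.
- **Collection as well.** End infection-AESI person-time at Year 4 in those sources, keep later suspected-related or fatal reports out of the rate analysis (they can be listed separately), and adjust or stratify the infection models by data source. This is a wording change. Its price is the late infection information from those sources: infection person-time falls to about 95%, 87% or 73% of the total if they hold 10%, 25% or 50% of patients.

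The decision should be made before the first patients in those sources reach Year 4, because infections not recorded then may not be recoverable.
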